5.6.2. Missing Safety Endpoints

Missing dates for AEs or concomitant medications will be imputed as described using the following rules:

- Partial start date:
 - Missing day only: Impute the first dose date if the year and the month of the AE start date are identical to those of the first dose date and also the AE end date is not prior to the first dose date; otherwise, impute the first day of the month.
 - Missing both day and month: Impute the first dose date if the year of the AE start date is identical to the year of the first dose date and also the AE end date is not prior to the first dose date; otherwise impute 1st January.
- Partial end date:
 - Missing day only: Impute/use the last day of the month or the last study date, whichever is earlier.
 - Missing day and month – Impute/use 31st December or the last study date, whichever is earlier.
- Completely missing start and end date or missing year: No imputation will be done.

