#### 6.1.1 Televisit #1a:

After signing the eIC, the following will be administered/obtained/collected by a trained assessor at televisit, unless otherwise noted ([Table 1](#)):

- Demographic information and Height
- Medical/Psychiatric/Social History
- Reproductive/Menstrual Cycle History Questionnaire; biological females only
- MINI-AS
- Prior Medications (past 12 months) and Concomitant Medications
- C-SSRS 'Baseline/Screening' Version
- Review Inclusion and Exclusion Criteria

	Protocol 812P413	
	Page 25 of 61	Version 2.0

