2. STUDY OBJECTIVES AND ENDPOINTS

2.1. Primary Objective and Endpoint

Primary Efficacy		
OBJECTIVES	ENDPOINTS	JUSTIFICATION FOR ENDPOINTS
The primary objective of this study is to evaluate the efficacy of Qelbree as a monotherapy and/or as an adjunctive therapy for ADHD symptoms in adults with ADHD and comorbid mood symptoms as measured by the clinician-rated ADHD Investigator Symptom Rating Scale (AISRS).	Change from baseline in AISRS total score by visit.	The AISRS is a clinician-rated scale that was validated for evaluating ADHD symptoms in adults in clinical trials per criteria outline in the DSM-5. The AISRS has been used in other clinical trials to evaluate the efficacy/safety of ADHD treatments, including the clinical trials of Qelbree in adults (Studies 812P306 and 812P311).

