6.5. Prior and Concomitant Medication

Prior and concomitant medications will be coded using the World Health Organization Drug Dictionary (WHO DD) version Global September 2023, and will be summarized descriptively by

the fourth level anatomical therapeutic chemical (ATC) classification and Preferred Name (PN), if applicable, using counts and percentages for the Safety Population. ATC fourth (ATC4) level is for the chemical, pharmacological or therapeutic subgroup. If an ATC4 level classification is not available for a coded term, the lowest available ATC level code will be substituted.

Prior medications are defined as those taken prior to first dose of study medication. Concomitant medications are those taken on or after start of study medication.

If a medication starts prior to the first dose and continues after the first dose it will be considered both prior and concomitant. Prior and concomitant medications will also be listed.

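### The SAP applies an adverse-event partial-date rule to medications, which can drop ongoing background drugs from the prior-medication table and count some stopped drugs as concomitant

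*SAP*

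**What the plan says.** SAP 5.6.2 sets one partial-date rule for two kinds of record: "Missing dates for AEs or concomitant medications will be imputed as described using the following rules". The start-date conditions that follow mention only AE dates. When day and month are both missing, the instruction is: "Impute the first dose date if the year of the AE start date is identical to the year of the first dose date", with the further condition that "the AE end date is not prior to the first dose date; otherwise impute 1st January". When only the day is missing, the month must match as well, and the fallback is the first of the month. Partial end dates go to the last day of the month, or to 31 December, unless the last study date is earlier. A missing year is not imputed.

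SAP 6.5 then classifies drugs by timing: "Prior medications are defined as those taken prior to first dose of study medication". Concomitant means taken on or after the start of study medication. A drug that starts before first dose and continues after it is both.

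Medication use is collected before dosing. Protocol 6.1.1 lists "Prior Medications (past 12 months) and Concomitant Medications" at Televisit 1a, and concomitant medications are reviewed again at Televisit 1b. Protocol 7.2 allows stimulants and most medications for mood symptoms.

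The primary objective in SAP 2.1 is to "evaluate the efficacy of Qelbree as a monotherapy and/or as an adjunctive therapy for ADHD symptoms". The readable text gives no rule for assigning participants to either use, and SAP 7.1 describes one summary for the whole Full Analysis Set (FAS).

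**The concern.** For an AE, moving an uncertain start to the first dose date is conservative, because it makes the event treatment-emergent. For a medication the same move works the other way: it removes use before treatment. A drug the participant reported taking at screening cannot have started on Day 1, yet the rule can date it so, and the SAP does not say that the screening record overrides the imputed date.

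In a single-arm, open-label study that allows stimulants and mood medication, the prior-medication table describes the background on which Qelbree was started. Undercounting that background, or counting a stopped drug as ongoing, blurs who was on what at first dose. The objective makes this of interest by naming monotherapy and adjunctive use.

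**Working it through.** The plan gives no figure to reproduce, so the check applies SAP 5.6.2 and then SAP 6.5 to test records, and sizes the affected share under stated assumptions.

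**Test records.** Assumed first dose 16 Oct 2024. Assumed last study date 98 days later (22 Jan 2025), so that cap does not bind. The end-date condition is tested on the imputed end date.

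| Recorded start | Recorded stop | Imputed | Class under SAP 6.5 | Correct? |
|---|---|---|---|---|
| 2019 | ongoing | from 1 Jan 2019 | prior + concomitant | yes |
| Mar 2024 | ongoing | from 1 Mar 2024 | prior + concomitant | yes |
| 2024 | ongoing | from 16 Oct 2024 | concomitant only | no, if in use at screening |
| Oct 2024 | ongoing | from 16 Oct 2024 | concomitant only | no, if in use at screening |
| 2024 | 1 Jun 2024 | 1 Jan to 1 Jun 2024 | prior only | yes |
| 2024 | Oct 2024 (true stop 5 Oct) | 16 to 31 Oct 2024 | concomitant only | no |
| 2019 | Oct 2024 (true stop 5 Oct) | 1 Jan 2019 to 31 Oct 2024 | prior + concomitant | wrongly concomitant |
| 2024 | 2024 | 16 Oct to 31 Dec 2024 | concomitant only | no, if stopped before first dose |

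Rows 3 and 4 are the start-date fault. Rows 6 to 8 are the end-date fault. In rows 6 and 8 the late end date also satisfies the end-date condition, so the start moves to Day 1 as well. The SAP does not say whether that condition uses the recorded or the imputed end date.

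**Share lost from the prior table.** Assumptions: the drug is ongoing; first dose is uniform over the 366 days of 2024; the true start is uniform over the 365 × Y days before first dose. A record is lost when its true start falls in the same calendar unit as the first dose, so

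share lost = (mean number of days in that unit before first dose) ÷ (365 × Y).

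- Year only: the mean number of earlier days in the year is (0 + 365)/2 = 182.5.
- Day missing: the mean number of earlier days in the month is (7 × 465 + 4 × 435 + 406)/366 = 5401/366 = 14.76. The terms are the sums of 0 to 30, 0 to 29 and 0 to 28 for months of 31, 30 and 29 days.

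| Y (years) | Year only | Day missing |
|---|---|---|
| 1 | 182.5/365 = 50% | 14.76/365 = 4.0% |
| 2 | 182.5/730 = 25% | 14.76/730 = 2.0% |
| 5 | 182.5/1825 = 10% | 14.76/1825 = 0.8% |
| 10 | 182.5/3650 = 5% | 14.76/3650 = 0.4% |

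A simulation with 200,000 draws per row gave 50/25/10/5% and 4.1/1.9/0.8/0.4%, which agrees up to simulation error. Each share is conditional on that type of partial date. Partial starts in an earlier month (with the month known) or an earlier year stay prior.

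**The case against.** Four points can fairly be made on the other side.

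- An ongoing drug is concomitant whether it is dated 1 January or Day 1. This stands: the start-date fault costs only the prior count.
- SAP 5.6.2 names concomitant medications, and SAP 6.5 defines prior by when the drug was taken, so a programmer could classify from the screening record alone. This is possible, but an ongoing drug is a concomitant medication and so falls under the imputation rule, and the SAP gives no order of precedence.
- SAP 6.5 plans counts by drug class and name, with listings. No table of newly started drugs is planned, so a false Day 1 start would not show in the concomitant counts. This stands.
- Imputing the earliest possible start for every medication would create the opposite error. With first dose on 16 Oct 2024, a drug first reported at Week 4 as started in Oct 2024 would be dated 1 Oct and called prior. This stands, and the remedy must separate the two situations.

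A reader might also infer that the rule corrupts a monotherapy/adjunctive split belonging to the primary objective. The documents do not support that. The objective gives no grouping rule, SAP 7.1 pools all FAS participants, and the exploratory sections are withheld. A split based on concomitant use would be untouched by the start-date rule; only one requiring a start before Day 1 would be affected. The end-date route is different: it could make a participant who had stopped a drug look adjunctive, if such a split were made.

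**Conclusion.** The point holds as a limited fault in a stated rule. Two kinds of record are misclassified: ongoing drugs whose partial start matches the first-dose month or year, which leave the prior table, and drugs stopped before first dose whose partial end date is imputed past it, which enter the concomitant table. The pooled AISRS analysis is unaffected.

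The size cannot be given as a count, because the number of partial dates is unknown. A reader might take 50% as the typical loss. It is the top of the range and requires every such drug to have started within a year of first dose. The protocol's 12-month look-back covers drugs taken in that period, not only those started in it, so longer-running drugs belong in the group and pull the share down. The shares rest on uniform starts and uniform first doses, which are assumptions. The importance is minor to moderate: the tables are descriptive, but the correction is cheap and should be settled before programming.

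**What to change.** Keep the present rule for AEs and give medications their own rule in SAP 5.6.2:

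- (a) A medication recorded at Televisit 1a or 1b as taken before first dose is prior whatever its imputed date. Its start is imputed to the earliest possible date, capped before first dose. The cap matters when first dose falls on the first of the month or on 1 January.
- (b) A medication first reported after first dose keeps the first-dose-date rule, unless its record shows earlier use.
- (c) A medication recorded at screening as stopped before first dose has its imputed end date capped before first dose.

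With (a), rows 3 and 4 of the test table become prior and concomitant. With (a) and (c), rows 6 to 8 become prior only, if the screening record shows that the drug had stopped.

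Because the primary objective names both uses, also define monotherapy and adjunctive status from medication use at first dose, stating which drug classes count. Show AISRS change descriptively for each group beside the pooled result, unless the withheld exploratory section already does so.

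The cost is a few lines of SAP text and one extra descriptive table with smaller groups, all from data already collected.

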**Footnotes:**

1. Virtual televisits will last between 45 to 120 minutes. Consent will occur on or before Telehealth Visit 1a.
2. Administer full/entire RMCH Questionnaire (1 up to 8 items) to biological females at Screening only (if not administered at Televisit #1a, administer at Televisit #1b).
3. Only administer the RMCH mQ5 to FOCPs at Televisit #2, #3, and #4 during Treatment [Week 4, Week 9, and Week 14/EOS, respectively].
4. All medications (especially stimulant or non-stimulant ADHD medications) taken 12 months prior to Screening.
5. BP/PR cuff (and UPT) will be shipped once participant is determined eligible. Prior to taking first dose, participant will measure and record BP/PR and weight (and confirm a negative UPT).
6. Weight will be collected with shoes off. BP/PR will be measured in a seated position. Self-reported by the participant to the study team on Day 1 and thereafter reported during scheduled televisits.
7. Height (with shoes off) will be self-reported to the study team.
8. Participant will need to report time, date, and dose of SM within the study mobile app on Day 1
9. PROs and questions about SM administration method and timing will be completed in the study mobile app.
10. At Week 14 the participant will be required to return all SM to Sponsor for destruction upon confirmation of proper SM accountability.
11. If participant discontinues early (Early-Termination), perform Week 14 assessments; however, ClinRO/PRO efficacy assessments should not be administered if participant has not taken daily dose of Qelbree for >7 consecutive days prior.

	Protocol 812P413	
	Page 30 of 61	Version 2.0

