## 7.2 Exclusion Criteria

A participant who meets any of the following criteria will be excluded from participation in the study:

1. Has a history of substance use disorder (alcohol, opioids, etc.) within the last 6 months prior to providing informed consent with exception of nicotine and cannabis.
2. Is currently taking or has taken Qelbree for treatment of ADHD in the last 3 months or is currently taking another non-stimulant medication for treatment of ADHD, like atomoxetine (Strattera), Clonidine (Catapres, Kapvay) or Guanfacine (Tenex, Intuniv). Stimulant medications for ADHD and most medications for mood symptoms (symptoms of depression and/or anxiety) are allowed.
3. Is taking a prohibited concomitant medication per the Qelbree Prescribing Information.
4. Is a FOCP who is pregnant, nursing, sexually active with a male partner and not willing to use one of the acceptable birth control methods throughout the study and/or is seeking fertility treatment.
5. Has history of moderate or severe head trauma or other neurological disorder or systemic medical disease that, in the Investigator's opinion, is likely to affect central nervous system functioning. This would include participants with:
  - a) A current diagnosis of a major neurological disorder; or
  - b) Seizures, seizure disorder or seizure-like events; or a history of seizure disorder within the immediate family (siblings, parents); or
  - c) Encephalopathy
6. Has attempted suicide within the 6 months prior to the C-SSRS assessment at Screening, or is at significant risk of suicide, either in the opinion of the Investigator or defined as a "yes" to suicidal ideation questions 4 or 5 or answering "yes" to suicidal behavior on the C-SSRS within the 6 months prior to the C-SSRS assessment at Screening.
7. Is currently participating in another clinical trial or has participated in a clinical trial within the 60 days prior to providing informed consent.
8. Has any history of schizophrenia, schizoaffective disorder, or bipolar disorder, or has any other psychiatric disorders in the Investigator's clinical judgement would interfere with their ability to participate in the study.
9. Has any unstable, clinically significant cardiovascular condition that in the Investigator's clinical judgement would preclude their participating in the study.

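### SAP 5.6.2 does not check imputed medication end dates against first dose, so a drug recorded as stopped beforehand can be tabulated as concomitant if its partial end date falls in the first-dose year or month

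*SAP*

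**What the plan says.** SAP 5.6.2 opens its date rules with "Missing dates for AEs or concomitant medications will be imputed as described using the following rules". For a partial end date:

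- Day missing: "Impute/use the last day of the month or the last study date, whichever is earlier".
- Day and month missing: "Impute/use 31st December or the last study date, whichever is earlier".
- Year missing: "Completely missing start and end date or missing year: No imputation will be done".

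The partial start-date rule does look at first dose. With day and month missing it reads "Impute the first dose date if the year of the AE start date is identical to the year of the first dose date", and it adds the condition that the end date is not before first dose. The end-date rule has no such condition.

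SAP 6.5 then sorts drugs by timing: "Concomitant medications are those taken on or after start of study medication". A drug that begins before first dose and runs past it is counted as both prior and concomitant.

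The protocol makes past drugs a routine part of the record. Table 1, footnote 4 asks for "All medications (especially stimulant or non-stimulant ADHD medications) taken 12 months prior to Screening". Protocol 6.1 allows a screening period of up to 28 days. Exclusion 2 in Protocol 7.2 bars a participant who has recently used the study drug "or is currently taking another non-stimulant medication for treatment of ADHD"; a non-stimulant of that kind that has already been stopped is not barred by that wording.

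**The concern.** The medication reviews at Televisits 1a and 1b can establish that a drug was stopped before Qelbree was started. If the record holds only a year, or a month and year, the end-date rule picks the latest possible day without regard to first dose. The imputed date can then contradict what was learned at the visit, and SAP 6.5 would place the drug among those taken with Qelbree.

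The concomitant-medication table is at stake, together with any description of participants as on monotherapy or adjunctive therapy that is drawn from it. The primary and safety objectives name that distinction. A participant who had properly stopped another non-stimulant before entry could appear in the table as taking it during treatment.

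**Working it through.** The plan gives no figure on this point, so there is none to reproduce. The check applies the stated rules to dates.

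**Worked case.** First dose 17 June 2024. The SAP does not define the last study date; it is taken here as Day 99, which is 17 June + 98 days = 23 September 2024. Any last study date on or after first dose gives the same classification.

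| Recorded stop | Imputed end date | Class under 6.5 |
|---|---|---|
| 2024 | min(31 Dec 2024, 23 Sep 2024) = 23 Sep 2024 | concomitant |
| 2023 | 31 Dec 2023 | prior only |
| June 2024 | 30 Jun 2024 | concomitant |
| May 2024 | 31 May 2024 | prior only |

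If start and end are both recorded only as 2024, and the start rule (worded for AEs) is used for drugs, the late end date satisfies the start rule's condition. The start becomes 17 June 2024, and the drug also drops out of the prior table.

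**How often, given a partial date.** Assumptions: the drug truly stopped before Televisit 1a; the stop date is uniform over the 365 days before it; the gap from Televisit 1a to first dose is *g* days, from 1 to 28; first dose is equally likely on each of the 366 days of 2024.

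For first dose on day *D* of the year, the stop falls in the same year in max(0, *D* − *g*) of 365 cases. With *g* = 14:

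- 15 January (*D* = 15): 1/365 = 0.3%
- 1 April (*D* = 92): 78/365 = 21.4%
- 1 July (*D* = 183): 169/365 = 46.3%
- 1 October (*D* = 275): 261/365 = 71.5%
- 15 December (*D* = 350): 336/365 = 92.1%

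Averaged over the year, with *m* = 366 − *g*, the share is [*m*(*m* + 1)/2] / (365 × 366):

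- *g* = 1: 66,795/133,590 = 50.0%
- *g* = 7: 64,620/133,590 = 48.4%
- *g* = 14: 62,128/133,590 = 46.5%
- *g* = 28: 57,291/133,590 = 42.9%

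With only the day missing, the stop must fall in the first-dose month. The same calendar count gives 4.0%, 2.6%, 1.3% and 0.0% for gaps of 1, 7, 14 and 28 days.

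Complete dates give 0%, and a missing year is not imputed.

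**The case against.** **Scope.** SAP 5.6.2 names AEs and concomitant medications, not prior ones, and the protocol schedule lists the two kinds of medication on separate rows. SAP 6.5 speaks of drugs taken, not of imputed dates, so a drug known to have stopped does not meet its definition. This stands in part: applying 5.6.2 to prior drugs is an inference. But no other rule covers a partly dated drug, its class depends on its dates, and classification is the only visible use of imputed medication dates. If 5.6.2 does not reach these drugs, the SAP has no rule for them.

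**Convention.** Taking the latest possible end date is a common cautious choice in safety tables. That stands for truly ambiguous records. It does not justify overriding a record that the drug had stopped.

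**Stronger readings.** A reader might infer four things that the documents do not support:

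- *That past drugs in general become concomitant.* Only partial end dates in the first-dose year or month do; earlier years and months stay prior.
- *That partial dates are frequent.* No share is given. A trained assessor takes the history, and Protocol 11.4 provides for logical checks and queries.
- *That efficacy results are distorted.* SAP 7.1 and 7.2 are single-group summaries, SAP 5.4 plans no covariate adjustment, and the readable text defines no monotherapy/adjunctive subgroup. The exploratory sections are not visible, so nothing can be drawn from them.
- *That false deviations for an excluded drug would arise.* SAP 6.2 takes deviations from those recorded in the EDC, not from imputed dates.

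**Conclusion.** The gap is real but narrow. As written, 5.6.2 can date a drug already recorded as stopped before first dose to a day after it, and 6.5 then tabulates it as concomitant. This needs a partial end date in the first-dose year with day and month missing, or in the first-dose month with the day missing.

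Among year-only stop dates, about 43% to 50% would be affected on average, depending heavily on when in the calendar year dosing starts. Among dates lacking only the day, the figure is about 0% to 4%. These shares rest on uniform stop dates and first-dose dates, and on the inference that 5.6.2 is used to classify prior drugs. The absolute number of records cannot be estimated and could be small.

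The damage is limited to descriptive medication tables and statements built on them. It is still worth correcting, because the tables could contradict information that the study already holds and the correction is cheap.

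**What to change.** State in SAP 5.6.2 that the date rules apply to prior and concomitant medications, keep the existing end-date rules, and add:

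> *If the medication is recorded as stopped before first dose (for example, at the Televisit 1a/1b medication review), the imputed end date is the earliest of the date given by the rule above, the date of the contact at which it was recorded as stopped, and the day before first dose. End dates are imputed before start dates, and prior/concomitant status is assigned afterwards.*

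In the worked case, suppose Televisit 1a was on 3 June 2024 and the stop is recorded as 2024. The end date becomes min(23 September, 3 June, 16 June) = 3 June 2024, so the drug is prior only. A year-only start of 2024 then becomes 1 January 2024, which keeps the drug in the prior table. A stop recorded as 2023 stays at 31 December 2023. The day-before-first-dose limit covers a drug stopped between Televisit 1b and first dose but reported later. Records whose stop relative to first dose is truly unknown stay under the current rule and count as concomitant.

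The cost is a short SAP addition and a small programming change, with no new visit. It relies on stopped/ongoing status being recorded for medications. Protocol 9.5.3 describes such an item for AEs, but the documents show none for medications, so the eCRF should be checked. A drug wrongly reported as stopped would not be counted as concomitant.
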